6.2. Analysis methods

Item 27a. What analysis method will be used and how will the treatment effects be presented

Analysis of *longitudinal the primary outcomes (FM)* will be conducted using a mixed linear regression model. Fixed effects are the time point, the intervention group, the interaction between time point and intervention group, ~~an indicator for the type of measurement used~~, and potential covariates (cf. Item 27b) ~~the covariates mentioned in Item 27b~~. Random effects are school, class, and child specific intercept and slope (with respect to time as a continuous covariate). The covariance matrix of the random intercept and the random slope is allowed to vary freely between the two intervention groups. The error variances are allowed to vary over time and between the intervention groups. ~~The error variance is allowed to vary between ADP and BIA measurements, and a constant difference in variance is assumed~~. The interaction between time point and intervention will be parametrized as time point specific intervention effects. The randomization will be taken into account by restricting the intervention effect at baseline to 0, ~~the difference of the variance of the random intercept between the intervention groups, and the difference in error variances at baseline between the intervention groups to 0~~.

Results of the *primary* analysis will be reported by the effect estimate together with a 95% confidence interval and a p-value of the null hypothesis of no intervention effect based on a Wald test. ~~The treatment effect will be phrased as "difference in mean change between the intervention and control group". In case of using log-transformed outcomes, the treatment effect will be transformed as $(\exp(.)-1)*100$ allowing an interpretation as the "difference in mean percentage change". The boundaries of the confidence interval will be transformed accordingly.~~

The structure of the model:

- Reflects the potential effects of school and classes on the outcome.
- Takes the correlation between measurements from the same child into account.
- ~~Allows using the known association of the primary outcome with height and a potential association with age or sex to increase the power by using them as covariates (if relevant)~~.
- Allows to include all children from the primary analysis population in the *primary* analysis independent of missing values in the *primary* outcome at some time point (including baseline) – ~~except for those missing the outcome at all time points~~.

- Requires only to assume missing at random (MAR) with respect to missing values in the primary outcome.
- Takes into account the use of two different measurement methods for the primary outcome.

Computations will be based on the default settings of the mixed command in Stata. In case of convergence problems, the complexity of the model will be reduced by the following steps until the convergence is reached: 1) Removal of variance components with estimates on the boundary. 2) Equal error variances across at the two follow up time points. 3) Equal error variances across the intervention groups. 4) Equal correlation between random intercept and random slope across the intervention groups.

The weights (estimated inverse probabilities of participation using register data, described in Item 27b) will be incorporated using the pweight option.

With respect to analyses using both BIA and BODPOD measurements, a corresponding bivariate model will be used (see sensitivity analysis, cf. section 27e). This will require modelling a potential systematic difference between the two measurements.

Item 27b. Any adjustment for covariates

The statistical power of RCTs can be improved by adjusting for (strong) prognostic factors. The approach described above implies already an adjustment for baseline variables. Consequently, there is only a need to adjust for factors which improve the prediction of the outcomes after adjustment for baseline values. Consequently, although FM and some of the secondary outcomes are known to be highly influenced by height, this does not necessarily imply a need to adjust for height.

The decision to adjust for potential prognostic factors will be based on an empirical investigation, whether the prediction of the outcome at the final time point can be improved by adding the factor to a model including the baseline values. Improvements of the adjusted R^2 by at least 0.1 will be regarded as an indicator for inclusion as covariate in the analysis model. The potential prognostic factors considered are height, weight, BMI, age and sex.

In case the use of inverse probability of participation weighting does not result in sufficient balance between the two intervention groups with respect to some factors, corresponding covariates may be added.

The primary outcome, FM, and some of the secondary outcomes are known to be highly influenced by the height of a child. It is hence intended to adjust for height. In the literature, an adjustment for the square of height is common. In an initial data analysis (cf. item 29), it will be checked whether this presents the optimal type of adjustment also in this population. Similarly, it is unclear whether there is an association of the outcomes (on the top of height) with age and sex to a degree, which implies an increase in the precision of the estimate for the intervention effect. Hence, the degree of association will also be investigated in an initial data analysis. The final decision about inclusion of these three variables and their functional form will be made based on the initial data analysis.

The following table represents the potential variables for an adjustment for the different outcomes:

| Outcome | Potential adjustment variables |
|--|--------------------------------|
| FM, FFM, % FFM, FFM-to-FM ratio, waist circumference | Height, age, sex |
| FM index, FFM index | Age, sex |
| Height z-score, BMI z-score | — |

As per CONSORT and since this is an RCT, besides adjustments listed above, results will be presented unadjusted.

Parental consent for participation was obtained after the schools' randomization results had been communicated. This has led to variation in participation rates between the intervention and control groups, suggesting a potential imbalance in participating characteristics. To adjust for this, background information available from Statistics Denmark, also for the children and parents who did not consent to participation, is used to model the probability of consenting as a function of background variables. This modelling is currently performed by Statistics Denmark and described in a separate document, which will be attached as supplement to the publication. The model will be used to derive inverse probability weights for each child participating as described by Li et al. (20,21). We will refer to these weights as "*inverse sampling probability weights*".

Item 27c. Methods used for assumptions to be checked for statistical methods

Check of univariate distributions

The distribution of any variable included in any later analysis will be depicted graphically in the overall population and stratified by age and sex. Time varying variables will be also stratified by time point of assessment, and the analysis will be extended to change scores, i.e. differences from baseline to follow-up.

Outliers will be identified visually, and data will be checked for potential explanations. In case of explanations indicating an undue effect of external factors, outliers might be removed. Any decision of this kind will be documented and included in the supplementary material of the paper.

Consistency checks of individual trajectories

For each longitudinal outcome, the individual longitudinal trajectories of each child will be inspected with respect to a uniform development. Suspicious measurements will be checked.

Check of expectations

The outcomes considered in this study are well-established. Population norms are available and associations with child characteristics are well-established. The distribution of these variables and their association with child characteristics in this study at baseline will be depicted and compared with data from the literature, for example national data on prevalence of childhood overweight and obesity (5), to establish the validity of the measurement methods and evaluate the representativeness of the study sample.

Item 27d. Details of alternative methods to be used if distributional assumptions do not hold, e.g., normality, proportional hazards, etc.

In case of skewed distributions or other anomalies, potential data transformations will be discussed, or additional sensitivity analyses will be defined.

Item 27e. Any planned sensitivity analyses for each outcome where applicable

To evaluate the robustness of our results to the method used to measure body composition, two sensitivity analyses will be conducted:

1. An ADP-only analysis: The analysis will be repeated using FM measured by ADP at baseline and end-of-study. This analysis will include only participants with a valid ADP measurement, i.e. those wearing standard clothing in the BODPOD.
2. A bivariate model combining ADP and BIA measurements at all time-points: This model will include up to five measurements of FM per child (ADP and BIA at baseline, BIA at interim, ADP and BIA at end-of-study).

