3.2. Randomization

Item 10. Randomization details, e.g., whether any minimization or stratification occurred (including stratifying factors used or the location of that information if it is not held within the SAP)

Randomization occurred at school level prior to inclusion of individual participants (i.e., children). A covariate-constrained randomization procedure was carried out to maximize school-level covariate balance between intervention and control group and to increase the probability that child baseline characteristics did not differ substantially between groups.

Allocation was conducted in two strata (1: Western Denmark, i.e. Region of Southern Denmark and 2: Eastern Denmark, i.e. Capital/Zealand Region) and was constrained by the following school-level covariates: Number of children in 1st and 2nd grade, proportion of children with parents of basic educational level (vocational education or lower), proportion of children with non-Danish background, rural or urban municipality, and number of planned weekly physical education lessons. The school-level covariates were obtained from the Ministry of Children and Education (10), and information on physical education lessons was provided by school principals. To ensure timely allocation of schools to their respective groups and allow schools sufficient time to plan the subsequent school year, randomization was conducted in two steps, with the first step based on the first 10 schools recruited, and the second step based on the last 14 schools recruited.

Randomization was performed using the 'cvcrand' command in STATA for covariate-constrained randomization in cluster-randomized trials (11). Randomization was carried out by a statistician not otherwise involved in the study, and the procedure was concealed from the investigators.

Due to the nature of the intervention, the study is open label, i.e. allocation is not blinded to participants, school staff, local communities, or research team members.

After randomization, one control school decided to withdraw from the study, leaving 12 intervention and 11 control schools in the study.

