5.5. Baseline characteristics

Item 25a. List of baseline characteristics to be summarized

Item 25b. Details of how baseline characteristics will be descriptively summarized

The following baseline characteristics will be summarized for the intervention versus control group:

- Cluster level (schools):
 - Number of participating school classes
 - Number of eligible children per school (median, IQR, range)
 - Mean proportion of parents with basic educational level in included year groups (%)
 - Mean proportion of parents with non-Danish background in included year groups (%)
 - Proportion of schools with urban vs rural location (%)
- Individual level (children):
 - Sex (male vs female) (n, %)
 - Age, years (median, IQR, range)
 - Grade level (1st, 2nd) (n, %)
 - Region (Eastern, Western) (n, %)
 - Sociodemographic characteristics:
 - Highest parental educational level (n, %)
 - Parental employment (n, %)
 - Family type (single vs two provider household) (n, %)
 - Country of origin (Danish or immigrant/descendant) (n, %)
 - Baseline body composition, measured by **bioimpedance (BIA)** (see further in Section 6.1, “Outcomes”) **air displacement plethysmography (ADP) with bioimpedance (BIA)** values used for missing data (see further in Section 6.1, “Outcomes” and Section 6.3 “Missing data”):
 - FM, kg (mean, SD or median, IQR (depending on distribution))

- FFM, kg (mean, SD or median, IQR (depending on distribution))
- FM index, kg/m² (mean, SD or median, IQR (depending on distribution))
- FFM index, kg/m² (mean, SD or median, IQR (depending on distribution))
- FFM-to-FM ratio (mean, SD or median, IQR (depending on distribution))
- Fat percentage, % (mean, SD or median, IQR (depending on distribution))
- Baseline anthropometry:
 - Height, cm (mean, SD or median, IQR (depending on distribution))
 - Height z-score (mean, SD or median, IQR (depending on distribution))
 - Weight, kg (mean, SD or median, IQR (depending on distribution))
 - BMI z-score based on WHO references (mean, SD or median, IQR (depending on distribution))
 - Prevalence of underweight, normal weight, overweight, obesity (n, %)
 - Waist circumference (mean, SD or median, IQR (depending on distribution))

Baseline characteristics of participants versus eligible non-participants:

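### Schools were allocated by region and in two steps, but the primary model has neither; the standard error is too large to the extent that they predict change in fat mass

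*SAP*

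**What the plan says.** SAP Section 3.2 describes the design. "Allocation was conducted in two strata", Western and Eastern Denmark, and "randomization was conducted in two steps, with the first step based on the first 10 schools recruited" and the second on the other 14. The steps had a practical purpose: "To ensure timely allocation of schools to their respective groups". Five school-level covariates also constrained the allocation. One control school then withdrew, "leaving 12 intervention and 11 control schools in the study".

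Section 6.2, Item 27a, gives the primary model: "Fixed effects are the time point, the intervention group, the interaction between time point and intervention group", plus potential covariates from Item 27b. The design enters in one place: "The randomization will be taken into account by restricting the intervention effect at baseline to 0". The result is reported with "a p-value of the null hypothesis of no intervention effect based on a Wald test", using Stata's default mixed settings and participation weights.

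Item 27b limits the candidate covariates to height, weight, BMI, age and sex. It lets others be added if weighting leaves the groups unbalanced. Region is a descriptive baseline variable in Section 5.5. Step does not appear after Section 3.2. No sensitivity analysis in Item 27e adds either factor. Section 6.4 applies the same model to the secondary outcomes.

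**The concern.** Balanced allocation within a factor removes that factor's contribution from the difference between arms. A model that omits the factor still leaves its contribution in the between-school variation from which the standard error is built. If the factor predicts the outcome, the reported standard error then exceeds the true one.

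The zero-baseline constraint does not repair this. Baseline values absorb stable regional differences in the level of fat mass, but a difference in change over the two school years stays in the school-level variation. The route for extra covariates in Item 27b does not repair it either, because it is optional and triggered by imbalance after weighting, not by the design.

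What is at stake is the width of the interval and some power. Bias is not at stake.

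**Working it through.** **1. Is there a figure to reproduce?** No. The SAP refers the sample size to the protocol and gives no SD, ICC or power. The size below rests on assumptions.

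**2. Inputs.** From the SAP: 23 schools (12 and 11), 1,359 children (Appendix 1), two-sided alpha 0.05. Children per school: m = 1,359/23 = 59. Assumed: school ICC after baseline of 0.01, 0.02 or 0.05, and share s of the between-school variance explained by region and step of 0, 25 or 50%. The region-by-step split is also assumed, for example West/East 6/4 in step 1 and 6/8 in step 2.

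**3. Formula.** The school component of the variance of a school mean is c = ICC / (ICC + (1 − ICC)/m). The factors explain R² = s × c of that variance. With balanced allocation, reported SE / true SE = 1/√(1 − R²), and the actual type I error is 2 × [1 − Φ(1.96/√(1 − R²))].

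Example for ICC 0.02 and s = 25%: c = 0.02/(0.02 + 0.98/59) = 0.547; R² = 0.137; SE ratio = 1/√0.863 = 1.08; type I error = 2 × [1 − Φ(2.11)] = 3.5%.

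| ICC | c | R², s = 25% | SE ratio | Type I | R², s = 50% | SE ratio | Type I |
|---|---|---|---|---|---|---|---|
| 0.01 | 0.374 | 0.093 | 1.05 | 4.0% | 0.187 | 1.11 | 3.0% |
| 0.02 | 0.547 | 0.137 | 1.08 | 3.5% | 0.273 | 1.17 | 2.1% |
| 0.05 | 0.757 | 0.189 | 1.11 | 3.0% | 0.378 | 1.27 | 1.3% |

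At s = 0 the ratio is 1 and type I error is 5%.

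**4. Simulation with a valid small-sample reference.** Child-level trials, 4,000 per setting, with 23 schools, three time points, weights, and data missing at the BIA rates of Table S1. The test uses a bias-corrected school-clustered variance with t on 21 df without the terms and 19 df with them. The fitted model approximates the weighted mixed model but is not identical to it. Ranges cover three assumed splits; slashes separate ICC 0.01/0.02/0.05.

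| Share | Type I without terms | Type I with terms | Power change from adding terms |
|---|---|---|---|
| 0% | 4.9–5.6% | 4.9–5.6% | −0.5 to −1.4 points |
| 25% | 3.9–4.4 / 3.9–4.6 / 3.2–4.3% | 4.7–5.7% | +1.3–2.3 / +3.3–3.7 / +4.1–5.1 points |
| 50% | 3.3–3.5 / 2.6–2.8 / 1.7–2.5% | 4.6–5.7% | +4–5 / +6–7 / +9–10 points |

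At 25% the interval with the terms is 3–4 / 5–6 / 8–9% narrower. The true SD of the estimate hardly moves (ratio with to without 0.979–1.015 at shares 0 to 25%), so the gain comes from a correct standard error. Simpler simulations on school means gave the same pattern.

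**5. The planned type of test.** With an uncorrected school-clustered Wald z, type I error without the terms is 7.0–8.7% at share 0%, 5.2–7.1% at 25% and 2.9–6.2% at 50%. With the terms it is 8.6–10.6% throughout. School-mean simulations gave about 8 to 10% with the terms. With few schools the z reference is too liberal, and each added school-level term makes it more so.

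**The case against.** **The effect may be nil.** The documents give no evidence that region or step predicts change in fat mass, and the steps were made so that schools could plan their year. This stands, and it limits the weight of the point.

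**The SAP states a rule.** Item 27b would adjust only for factors that improve prediction after baseline, and says results are otherwise unadjusted (that sentence may be left over from SAP version 1). The rule is general, but it is applied to child factors, with a threshold of 0.1 in adjusted R². At an ICC of 0.05 or less, a school-level factor explains at most about 5% of the variance that remains after baseline, so it would fail the screen even if it explained all differences between schools. The screen does not settle the question for a design factor.

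**Against the planned test, the terms alone do harm.** This is correct and decides the form of the fix. A reader might infer that the planned test is conservative. The figures in step 5 do not support that: the liberal z reference pulls the other way, and the net result depends on unknown inputs.

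**A large loss of power.** A reader might put R² = 0.5 into the formula and find a standard error 41% too large. That R² refers to the whole variance of school means. It would need a share of 0.5/0.547 = 91% at ICC 0.02 and 0.5/0.374 = 134% at ICC 0.01, which is impossible.

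**The remedy is selective.** The five constraining covariates also shaped the allocation, and some are at least as plausible as predictors. This stands. Adding region and step does not make the standard error reflect all the balance achieved.

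**Conclusion.** The omission is real: region and step shaped the allocation, and neither is in the model, the candidate covariates or the sensitivity analyses. The estimate is unbiased. If these factors predict change in fat mass, a model-based or school-clustered standard error is too large and, with a valid small-sample reference, the test is conservative. At an assumed 25% share of between-school variance, type I error is about 3 to 4.5%, and adding the terms returns roughly 1 to 5 points of power.

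These figures rest on assumed ICCs, shares and region-by-step splits. The true share may be near zero. The document does not support a claim that the primary result would be invalid, or that the planned Wald z is conservative. This is a point to consider, and it is tied to the small-sample reference for 23 schools.

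**What to change.** In Item 27a, make two changes together:

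1. Pre-specify region (stratum) and randomization step, each interacted with time point, as fixed effects in the primary model and the continuous secondary models.
2. Replace the Wald z with a small-sample reference that works with the weights, for example a bias-corrected school-clustered variance with t on about 19 df (23 schools less intercept, intervention, region and step).

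Do not make the first change alone. If no such variance is available for the weighted mixed model, or if effect analyses have begun, keep the primary model and report the adjusted model as a sensitivity analysis. If region and step stay out, Item 27b should say so and give the reason.

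**Cost.** SAP wording and some programming, since Appendix 1 (Section 4.2) already notes limits of the mixed command with weights. Both factors are known for every school. If they are not prognostic, the price is 2 school-level df (21 to 19), an interval 0.5–1.5% wider and about 1 point of power. The five constraining covariates stay out to save degrees of freedom, so any conservatism from balancing them remains.

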3.1. Trial design

Item 9. Brief description of trial design, including type of trial (e.g., parallel group, multi-arm, crossover, factorial) and allocation ratio and may include brief description of interventions.

The GHK trial is a parallel group cluster-randomized superiority trial with two arms. A total of 24 schools were randomly allocated in a 1:1 ratio to intervention (the GHK multi-component intervention program) or control (no intervention). The intervention is described in detail in (2).

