4.1. Confidence intervals and P values

Item 16. Level of statistical significance

All hypotheses testing will be based on two-sided tests at the alpha = 0.05 level.

Item 17. Description and rationale for any adjustment for multiplicity and, if so, detailing how the type 1 error is to be controlled

No adjustment for multiplicity will be performed.

Item 18. Confidence intervals to be reported

All confidence intervals presented will be 95% and two-sided.

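### The primary Wald test and 95% CI rest on 23 schools but have no small-sample reference or variance, so the 0.05 level and 95% coverage are not secured

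*SAP*

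**What the plan says.** Section 3.1 of the SAP states "A total of 24 schools were randomly allocated in a 1:1 ratio". Section 3.2 reports the withdrawal of one control school, "leaving 12 intervention and 11 control schools in the study". The same section says that allocation was stratified by region and "constrained by the following school-level covariates": the number of children in the two grades, parental education, non-Danish background, rural or urban municipality, and physical education lessons. It adds that "randomization was conducted in two steps, with the first step based on the first 10 schools recruited" and the second on the remaining 14.

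Section 4.1 sets the error rates: "All hypotheses testing will be based on two-sided tests at the alpha = 0.05 level" and "All confidence intervals presented will be 95% and two-sided".

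Section 6.2, Item 27a, fits a linear mixed model with school, class and child random effects. The result is reported as an estimate, a 95% confidence interval and a "p-value of the null hypothesis of no intervention effect based on a Wald test". On computation it says "Computations will be based on the default settings of the mixed command in Stata", and it brings in the participation weights through pweight.

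No section gives the reference distribution of the Wald statistic, its degrees of freedom, a restricted-likelihood option or a small-sample variance correction. The covariate candidates in Item 27b are height, weight, BMI, age and sex, all at child level. Item 27b also allows covariates to be added for factors that remain unbalanced after weighting.

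**The concern.** Schools were randomized, so the precision of the treatment comparison is limited by the number of schools and not by the 1,359 children. With 23 schools, a normal critical value of 1.960 is too small against a t distribution on 21 degrees of freedom. An uncorrected cluster-robust standard error is also biased downwards. Both make the test liberal.

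Constrained allocation works the other way. It balances the arms on school-level covariates. If those covariates predict the outcome but are left out of the model, the standard error still carries variation that the design has removed, and the test becomes conservative.

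The SAP sets neither effect down and gives nothing to show which one dominates. What is at stake is the calibration of the primary p-value and the coverage of the published interval. If the choice between z and t were left until a borderline result was known, it would be driven by the data.

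**Working it through.** **Inputs from the SAP.** Two-sided alpha 0.05 and 95% intervals (Section 4.1); 12 and 11 schools (Section 3.2); 1,359 children in the analysis population, 1,197 of them with bioimpedance data at end of study (Appendix 1, Table S1); Wald test, default settings and pweight (Item 27a).

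**Assumed, because the SAP does not say.** Normal reference distribution; school-clustered sandwich standard error; ICC, spread of school sizes and weights, prognostic share of the constraint covariates, and the fraction of allocations kept by the constraint.

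**1. The plan's own figure.** A size of 0.05 at the critical value 1.960 is reproduced only with an infinite-df (normal) reference.

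**2. Normal against t.** School-level df = 12 + 11 − 2 = 21.
- P(|t21| > 1.960) = 0.0634, so a nominal 95% interval covers 93.7%.
- The t21 critical value is 2.080, and 2.080 / 1.960 = 1.061.

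**3. Sandwich bias, equal-sized schools.**
- Expected sandwich variance (in units of σ²) = (11/12)/12 + (10/11)/11 = 0.1590.
- True variance = 1/12 + 1/11 = 0.1742.
- SE ratio, unscaled = √(0.1590/0.1742) = 0.955. Scaled by 23/22 it is 0.955 × √(23/22) = 0.977.
- Size with z, scaled: P(|t21| > 1.960 × 0.977) = 0.069. Unscaled: P(|t21| > 1.960 × 0.955) = 0.075.

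Steps 2 and 3 together give 6.3% to 7.5% under simple randomization.

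**4. Simulation check, simple randomization.** One school-level effect, 1,359 children, school-size CV 0.3 to 0.5, 10,000 trials per setting. Ranges run over ICC 0.01 to 0.10.

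| Method | Size |
|---|---|
| Maximum likelihood, z | 0.073–0.082 |
| Restricted likelihood, z | 0.062–0.069 |
| School sandwich, z | 0.067–0.078 |
| Restricted likelihood, t21 | 0.048–0.055 |
| School sandwich, t21 | 0.053–0.064 |

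At ICC 0, model-based maximum likelihood with z is not inflated (0.044–0.046), but the sandwich with z still is (0.072–0.074).

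**5. Simulation, constrained allocation.** Two steps of 10 and 14 schools, assumed strata of 6+4 and 6+8, five constraining covariates left out of the model, one control school dropped, three time points, 1,197 children, school-size CV and weight CV 0.4. The test is the scaled sandwich with z. Each cell gives ICC 0.01 / 0.03 / 0.10.

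| Share of between-school variance explained | Best 10% of allocations kept | Best 50% kept |
|---|---|---|
| 10% | 0.061 / 0.063 / 0.061 | 0.069 / 0.064 / 0.069 |
| 30% | 0.055 / 0.051 / 0.048 | 0.062 / 0.055 / 0.054 |
| 50% | 0.051 / 0.039 / 0.031 | 0.056 / 0.054 / 0.049 |

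The range is 3.1% to 6.9%, on both sides of 5%. Monte Carlo error is about 0.002 to 0.003. The working covariance was taken as known, so these figures are indicative.

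**6. Where the verdict changes.** Nominal p at which the corrected test just reaches 0.05:
- Plain t21: 2 × P(Z > 2.080) = 0.038.
- Bias-reduced variance with t21: 2.080 / 0.977 = 2.129, and 2 × P(Z > 2.129) = 0.033.

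A nominal p between these values and 0.05 loses significance.

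**7. Interval width against scaled sandwich with z.** Plain t21: 1.061. Bias-reduced with t21: 1.061 / 0.977 = 1.086.

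**The case against.** The strongest objection is that a reader might infer a proven inflation of the type I error, and the documents do not support that. The 6.3% to 7.5% range belongs to simple randomization, whereas Section 3.2 describes constrained allocation. In the 18 constrained settings above, 10 lie at or below 5.5% and 4 at or below 5.0%. This stands, and it limits the claim to error rates that are not secured.

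The constrained-allocation figures also rest on assumed strata, prognostic shares and ICCs, and the simple-randomization check in step 4 does not cover them. The software reading is an assumption too. Appendix 1 mentions limitations arising from the mixed command and the weights, so the settings were not chosen without thought, but it offers no remedy for this one.

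Two further inferences should be resisted. The loss of one school is not the cause: the critical value is 2.074 on 22 df and 2.080 on 21. Nor can a much larger error be argued from a model that holds all five constraint covariates, because the SAP does not list them for the model.

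Finally, the correction does not restore exactly 5% everywhere. In the constrained settings with covariates left out, plain t21 runs at 2.4% to 5.6% and bias-reduced t21 at 2.1% to 5.0%. That is true, but the departure is then mainly on the conservative side.

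**Conclusion.** The concern holds as a gap in calibration. Item 27a fixes the primary test and interval without a small-sample reference or variance for a comparison of 23 schools, and nothing else in the SAP supplies one. The leave-one-school-out analysis in Item 27e examines influence, not calibration.

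On the assumed reading of the defaults, size is about 6.3% to 7.5% under simple randomization. Under the constrained allocation with its covariates omitted, it is about 3% to 7%. The direction of the error in this trial cannot be settled from the document. The point estimate is untouched, and the practical reach is a nominal primary p of about 0.03 to 0.05 and the width of the reported interval. It should be fixed but does not threaten the trial. Confidence is good for the missing specification and the closed-form figures, and moderate for the constrained-allocation range.

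**What to change.** In Item 27a, state the variance estimator, reference distribution and degrees of freedom for the weighted primary model. A suitable choice is a school-clustered variance, preferably bias-reduced, with a t reference on school-level degrees of freedom: 23 − 2 = 21, less one for each school-level covariate in the model. Use the same basis for the p-value and the confidence interval. In Item 27b, state whether the constraint covariates of Section 3.2 enter the primary model.

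The cost is a few lines of wording and a short calculation. Intervals become about 6% wider with plain t21, or about 9% wider with the bias-reduced variance, and p-values rise slightly. If strongly prognostic constraint covariates are left out, the test will be conservative and some power is lost. Plain t21 on the uncorrected sandwich is the minimum acceptable change: it gives about 5.5% in the closed form for simple randomization (P(|t21| > 2.080 × 0.977) = 0.055).
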